| D. | Aims 2 & 3 analysis | 24 |
| E. | Presentation and manuscript preparation | 25 |
| F. | Project website..... | 25 |
| G. | Public announcements..... | 25 |
| VI. Financial Policies and Procedures..... | | 26 |
| A. | General financial management | 26 |
| B. | Purchasing | 26 |
| C. | Subcontractor invoicing..... | 26 |
| D. | Participant payment | 26 |
| VII. Reporting Requirements..... | | 28 |
| A. | PCORI reporting | 28 |
| B. | Institutional reporting..... | 28 |
| C. | Risk Management and Adverse Event Reporting..... | 28 |
| D. | Research and financial misconduct | 28 |
| E. | Study completion and closeout procedures | 28 |

I. Overview

A. Project aims

The VOICe project, funded by the [Patient-Centered Outcomes Research Institute](#), will determine if group concept mapping (GCM), a structured brainstorming process, is a comprehensive and efficient method of identifying outcomes that are important to patients by comparing it to one-on-one interviews (the "gold standard"). The overarching objective of this methodology study is to provide high quality evidence to researchers, clinicians and policy makers about two methods used to elicit patient preferences for outcomes in order to inform best-practices for designing patient-centered research studies.

Aim 1: To engage patients to identify their own patient-important outcomes for managing their chronic conditions through 1) one-on-one interviews and 2) concept mapping groups.

Aim 2: To compare the comprehensiveness of concept mapping to one-on-one interviews for identifying patient-important outcomes for managing their chronic conditions.

Aim 3: To compare the efficiency of concept mapping to one-on-one interviews for identifying patient important outcomes for managing their chronic conditions.

B. Primary Outcomes

Primary outcomes:

1. Comprehensiveness of interviews as compared to one concept mapping group
2. Comprehensiveness of interviews as compared to three concept mapping groups
3. Comprehensiveness of concept mapping

Secondary outcomes: Efficiency of interviews compared to GCM

C. Timeline and key milestones

Project timeline: January 1, 2016- December 31, 2018.

- Year 1: All training and interview activities will occur during the first year of the project.
Year 2: Final interview analysis and concept mapping sessions will occur during the second year.
Year 3: Abstract preparation will and dissemination of the results will occur in the final year of the project.

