| C6 | Completion of 75% of interview recruitment and participation | 
 • Recruit interview participants • Complete open-ended, semi-structured qualitative interviews (total goal n=90-120, 75% goal n=67-90) | 12/31/2016 |
| C | Report Submission | Submit Progress Report, Using Interim Progress Report template | 12/31/2016 |
| D1 | PAKSAB: Concept Mapping material preparation | 
 • Develop Concept Mapping prompt • Plan recruitment process | 3/31/2017 |
| D2 | Completion of 100% of interview recruitment and participation | 
 • Recruit interview participants • Complete open-ended, semi-structured qualitative interviews (total goal n=90-120) | 3/31/2017 |
| D3 | Completion of 75% of one-on-one interview analysis | 
 • Complete coding and initial analysis of 75% participant interviews (total goal n=90-120, 75% goal n=67-90) | 3/31/2017 |
| F6 | Dissemination of results | 
 • Submit CM manuscript • Present interview abstract in at least 1 national conference (pending acceptance from submissions with target date 9/30/17)) • Update project-specific website within Jefferson domain | 6/30/2018 |

VOICe Study Procedures Manual V.6

| | | | |
|----|--|--|-------------------|
| D4 | Completion of 100% of interview analysis | 
 • Complete coding and initial analysis of 100% participant interviews (total goal n=90-120) | 6/30/2017 |
| D5 | PAKSAB: Interim Report | 
 • Generate interim progress report for PCORI | 6/30/2017 |
| D | Report Submission | Submit Progress Report, Using Interim Progress Report template | 6/30/2017 |
| E1 | Interview abstract submission and manuscript preparation | 
 • Prepare and submit abstract from interview data • Begin preparation of manuscript from interview | 9/30/2017 |
| E2 | PAKSAB: Interview analysis and abstract | 
 • Complete final interview analysis • Submit interview abstract to PCORI | 9/30/2017 |
| E3 | Concept Mapping preparation | 
 • Complete recruitment of 25 participants per group (n=75) • Schedule CM groups • Train study personnel in CM methods | 9/30/2017 |

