| E4 | Concept Mapping data collection | 
 • Conduct 3 sessions for each CM group (n=3CM groups, n= 60 participants) | 12/31/2017 |
| E5 | PAKSAB: CM result discussion | 
 • Discuss initial CM results | 12/31/2017 |
| E6 | Dissemination of results | 
 • Update project-specific website within Jefferson domain – include members of team, overall project goals, links to any publications (once available) | 12/31/2017 |
| E | Report Submission | Submit Progress Report, Using Interim Progress Report template | 12/31/2017 |
| F1 | Analysis Aims 2 & 3: Start | 
 • Begin assessments for Aims 2 & 3 (comprehensiveness and efficiency) | 3/31/2018 |
| F2 | PAKSAB Y3 Q1: Synthesis and reporting | 
Convene PAKSAB to complete the following:
 
 • Discuss final CM results • Prepare/submit CM abstract • Begin preparation of CM manuscript • Begin development of dissemination plan with DAT | 3/31/2018 |
| F3 | Analysis Aims 2 & 3: Finalize | 
 • Complete assessments for Aims 2 & 3 (comprehensiveness and efficiency) | 6/30/2018 |
| F4 | CM manuscript completion | 
 • Complete draft of CM manuscript | 6/30/2018 |
| F5 | PAKSAB Y3 Q2: Synthesis and reporting | 
Convene PAKSAB to complete the following:
 
 • Review CM manuscript and decide on journal for submission • Refine results for Aims 2 & 3 • Develop dissemination plan with DAT • Plan next steps planning | 6/30/2018 |

| | | | |
|----------|---|--|--|
| F7 | PAKSAB: Results delivery | 
 • Deliver CM results to PCORI • Deliver results from Aims 2& 3 to PCORI • Generate interim progress report for PCORI | 6/30/2018 |
| F | Report Submission | Submit Progress Report, Using Interim Progress Report template | 6/30/2018 |
| G1 | Abstract and manuscript for Aims 1,2 & 3 | 
 • Prepare and submit abstract for Aims 1,2 & 3 • Prepare and submit manuscript for Aims 1,2 & 3 | 9/30/2018 |
| G2 | PAKSAB Y3 Q3: Synthesis and reporting | 
Convene PAKSAB to complete the following:
 
 • Review CM manuscript • Refine results for Aims 2 & 3 • Develop dissemination plan with DAT • Plan next steps • Review manuscript for Aims 2 & 3 | 9/30/2018 |

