2. Make sure that tax will not be applied to the delivery if using a p-card to pay for the order
3. Keep the receipts and turn them in to the p-card administrator

Patient Remuneration

1. Reach out to your Greenphire contact to get Greenphire training and your login id/password for the ClinCard system (this is NOT your Jeff sign-in info)
2. Email Greenphire contact with the following information: study title, JeffTrial #, Jefferson account number that is paying for the study, the payment schedule, and the number of cards that you need
3. Pick up the remuneration cards from Greenphire contact

Setting up the space:

1. Talk to the security desk. Have 2-3 people waiting in the lobby of the building to greet and direct participants to the meeting room
2. Set up refreshment table. Have 3+ people in room (with refreshments) to check participants in with sign in sheet, then to obtain informed consent, and finally to distribute demographic forms and W9s. Have the person who is collecting the forms check for completeness
3. To set up the brainstorming room, make sure that the projector and computer are working, and pull up a blank word document to record all of the responses – immediately save the document

SESSION 1:

Materials:

- Sign at the security desk (“Check in here”, project coordinator and PI cell)
- Signs at both entrances of the building (“CM sessions inside”, project coordinator and PI cell” “Use the 9th st entrance around the corner”)
- Sign-in sheet
- Breakfast
- Recorders
- Schedule of events for team members (Roles to be assigned: 2 people as greeters, 3+ people to obtain informed consent, 1 research team member and 1 PAKSAB member to moderate the discussion, 1 person to record the brainstorming list, 1 person to accept/set up food order while brainstorming is in progress, 3-4 people to set up computers and explain sorting, and 2 people to distribute remuneration cards)
- 3 Folders, labelled as follows: Demographic Forms, W-9s + receipts, Informed Consent
- Patient packets (2 copies of informed consent, demographic form, ClinCards/ informational brochures, receipt template for each card, W9)
- ClinCard tracking log
- pens + notecards for optional written brainstorming
- pens for consenting
- Printed prompt for each participant
- Printed sorting instructions for each participant.
- Example sorting sheet

Steps:

1. **Check in process**

- Check in person to mark that patient is present and give name tag with assigned participant number

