In the past, medical research has often focused on asking doctors what they think is most important in improving health care for their patients, but we have realized that patients may have different priorities and objectives when they seek health care. Today we would like to know what things patients think about when deciding whether their diabetes treatment has been successful. It can be anything patients consider important, including little things that matter on a day to day basis or things that patients might want to happen in the long term. We hope to use this information to improve the delivery of health care and prioritize the concerns patients tell us are important them.

So with this in mind, the question I’d like to ask is: *You are here as a person with diabetes; when people with diabetes seek care, what are they hoping to change or improve?”*

The moderator begins the discussion. As the responses are listed, the moderator dictates responses to the recorder, and the recorder types them into a list that is projected in front of all of the participants. Responses are collected until the session reaches theme saturation.

3. After the session, the team members clarify all of the items on the list to ensure that they are written in a consistent format. In the GCM software, make sure that brainstorming is active (under project settings) and upload the list as a text (txt) file into the software.
4. The Excel spreadsheet will then be uploaded to the Concept Systems Global Software and “sort cards” will be generated. These cards each contain one statement generated from the brainstorming session, and will be loaded into the Concept Systems Global Software for the second session.
5. Two individuals should set up lunch towards the end of Session 1.

SESSION 2:

Materials:

1. Sign-in sheet
2. Food
3. Meeting space with a computer for each participant
4. Sorting example sheet for each participant

Prep Steps:

1. Add participant ID into the software
2. Set up a participant ids (these must be unique for each project that is put on the same license) in the system for each participant within the CS software
3. Input rating question(s) into the software
4. Print out sorting example sheet for each participant
5. Print out of rules for each participant
6. Before the second session begins, de-select brainstorming and select the rating and sorting sections (on the project settings tab) within the GCM software.

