We will use a conventional content analysis approach for the analysis of the semi-structured interviews with the purpose of classifying the interview text into distinct categories that represent similar meanings and allowing themes to emerge from the data. [name] will oversee this analysis, and work with a coding team of four others (Project Coordinator, Research Assistant, and 2 PAKSAB members) to train them for coding interviews. The coding team will meet regularly during this process with the co-PIs to discuss codes and ideas that arise during coding.

Each transcript will be labeled with the participant's demographic and illness characteristics as well as the location along the care continuum at which the data were collected (acute, post-acute, primary care) and the mode of data collection (phone, in person). Transcripts from the same care continuum location will be analyzed together. Transcripts will be coded by members of the research team with a content analysis approach to identify thematic clusters within each set of care continuum location. Once data are coded, we will use the query function in NVivo to sort the data by various patient characteristics to examine patterns.

C. Concept mapping analysis

Data from each of the three CM groups will be entered into Concept Systems Global Software separately, with initial thematic clusters generated by the software and final clusters determined by the CM participants within each group. Each CM group will include participants from all three locations on the care continuum (acute, post-acute, primary care), thus generating three final sets of location-agnostic themes.

D. Aims 2 & 3 analysis

For Aims 2 & 3, we are comparing the comprehensiveness and efficiency of interviews and concept mapping.

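### Team members who may know the interview themes dictate and edit the concept mapping statements, with no limit on edits and no check against what was said

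*Combined protocol and SAP*

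**What the plan says.** **Order of work.** Section I.C states that "Final interview analysis and concept mapping sessions will occur during the second year". Milestone D4, due 6/30/2017, reads "Complete coding and initial analysis of 100% participant interviews (total goal n=90-120". Milestone E2, due 9/30/2017, includes "Complete final interview analysis". Milestone E4, due 12/31/2017, is "Conduct 3 sessions for each CM group (n=3CM groups, n= 60 participants". Section IV.ii lists the CM dates as 9/23 and 9/25, 11/11 and 11/13, and 12/2 and 12/4, without a year.

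**People.** Section V.B has a lead who will "work with a coding team of four others (Project Coordinator, Research Assistant, and 2 PAKSAB members"; this team also meets regularly with the co-PIs. The PAKSAB milestones include reviewing transcripts and generating the codebook (C2), reviewing the first coding results (C5), developing the CM prompt (D1) and the final interview analysis (E2). For CM Session 1, section IV.iii assigns "1 research team member and 1 PAKSAB member to moderate the discussion". The training section lists CM training under the Project Coordinator and Research Assistants.

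**Handling of statements.** In Session 1 the moderator dictates each response and a recorder types it on screen in view of the group. "Responses are collected until the session reaches theme saturation". Step 3 then says "After the session, the team members clarify all of the items on the list to ensure that they are written in a consistent format", after which the list is uploaded and made into sort cards.

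**Measure.** Section V.D reports, for each interview setting, the proportion of interview themes that appear in the CM list. It does this first for CM group 1 and then for the three groups combined.

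**The concern.** Aim 2 treats the CM list as what patients produced without help from the interviews. By the time that list is made, the interview themes exist, and people in the coding or reviewing roles may know them. If a moderator dictates a response in the language of a known theme, or an editor clarifies a vague item in that direction, a theme that would have been scored absent is scored present.

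The comprehensiveness outcomes that compare interviews with one CM group and with three both rest on these lists. Pooling three groups does not cancel an error that tends in one direction. The reported proportion would look the same whether patients raised a theme or the team's wording supplied it. The person judging the match is not blinded either.

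**Working it through.** The plan has no sample-size, alpha or power figure on this point, because the comparison is descriptive. I checked three things.

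**1. Timing.** The year of the CM sessions is inferred as 2017 from milestone E4. The listed dates are Saturday and Monday pairs in 2017.

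| CM group | First date | Days after D4 (6/30/2017) | Days from E2 (9/30/2017) |
|---|---|---|---|
| 1 | 9/23 | 85 | 7 before |
| 2 | 11/11 | 134 | 42 after |
| 3 | 12/2 | 155 | 63 after |

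Coding and initial analysis are due before every group. The final interview analysis is due after both dates of group 1, and section V.D compares CM with the final interview themes.

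**2. Points of entry.** Set side by side, the sections show two documented steps at which the team's wording enters the CM list:

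- dictation by the moderator, which shapes even the first typed version;
- clarification after Session 1, whose stated purpose is format but for which no permitted or forbidden change is given.

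The introduction script in section IV.iii places brainstorming in the morning and the second activity the same afternoon. Clarification therefore has to be done within hours. The Word document is saved at the start of Session 1, but nothing requires an unedited copy to be kept or compared. The data table in section II.C lists interview audio but not CM audio, although recorders are among the Session 1 materials.

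**3. Direction and possible size.** Let p be the share of interview themes that CM would find unaided, and c the share of the missed themes that enter the list by carry-over. With the interview themes held fixed:

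observed proportion = p + (1 − p) × c, so the increase is (1 − p) × c, which is never negative.

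Both p and c are assumptions; the documents give no theme counts.

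| p | c = 0.10 | c = 0.25 | c = 0.50 |
|---|---|---|---|
| 0.50 | 0.55 | 0.625 | 0.75 |
| 0.70 | 0.73 | 0.775 | 0.85 |
| 0.90 | 0.91 | 0.925 | 0.95 |

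The increase runs from (1 − 0.90) × 0.10 = 0.01 to (1 − 0.50) × 0.50 = 0.25, that is, 1 to 25 percentage points. In counts, suppose a setting has 20 themes and CM truly raises 14: 14/20 = 70%. Two carried-over themes give 16/20 = 80%, and three give 17/20 = 85%.

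**The case against.** The case against has real substance.

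- **Safeguards exist.** Participants may first write down their own ideas (marked optional). Colleagues write down what is said aloud. The list is projected as it is typed, so a wrong dictation is visible. Participants sort every card, and in Session 3 they hear each statement, name the clusters and can move items. This stands as a partial defence. None of it compares an edited card with the original remark.
- **The clarification step is described modestly.** Its purpose is consistent format, and each card is meant to hold a statement from the brainstorming. A reader might infer that the team rewrites every statement; the text does not say so. What stands is that no limit is set.
- **Other routes are not documented.** A reader might infer that moderators probe toward known themes, or that the moderator decides when saturation is reached. The manual gives a scripted introduction and one fixed question, describes no probing, and does not say who judges saturation. An early stop could also lower coverage. I do not rely on either route.
- **The same individuals are not shown to do both jobs.** Names are removed, only selected PAKSAB members lead sessions, and part of the team-roles section (I.D) is not in the text available to me. What is shown is overlap of roles, with no separation required in the text that can be read.
- **The traffic is not strictly one-way.** Because E2 falls after group 1, CM content could also reach the final interview themes. That could merge, split or add themes, so I give it no direction.
- **Excluding coders would not give moderators who are unaware of the themes**, because PAKSAB exposure is wider than the coding team, and it would displace trained staff. This stands, and the fix does not depend on it.

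**Conclusion.** The concern holds as an uncontrolled risk to the Aim 2 comparisons, not as a demonstrated bias. Coding and initial analysis are scheduled to finish before CM begins, the same roles supply both activities, and two documented steps let the team's wording into the CM list without an edit rule or a check. Carry-over at those steps would tend to raise the proportion of interview themes found.

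Its size is unknown; the 1 to 25 points rest wholly on assumed p and c. The dating rests on reading the session dates as 2017. The documents do not support a claim that every bias in the process must run upward, or that CM cannot influence the interview themes. A change is still worthwhile, because the planned output could not reveal the problem and prevention is cheap.

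**What to change.** 1. **Section IV.iii, Session 1, step 3.** Save and freeze the projected Word list as typed, before clarification. Limit clarification to grammar, format and splitting compound items, and keep an edit log.
2. **Section V.D.** Keep the planned comparison. Beside it, report the proportion of interview themes present in the frozen list. Where a match depends on an edited statement, check it against the Session 1 recording or the colleagues' written notes, and report the proportion with and without such matches. Add the CM recordings and notes to the data table in section II.C so that they are kept for this purpose.
3. **Sections I.C and V.B.** Lock the interview theme list for each setting before CM group 1 meets. This means bringing that part of E2 forward by at least 7 days.
4. **Staffing.** Where possible, have the clarification done by listed team members who did not code interviews. This is a preference, not a requirement.

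The cost is one saved file, an edit log, a second tabulation, a short audio check and an earlier lock of the interview themes. The planned primary comparison is unchanged.

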After initial explanation of what the study is about, the research team will review an additional screening form to ensure exclusion criteria will not prevent them from participating in the study. The research team members will document in the One Drive Excel sheet when patients a) initially appear eligible but are then found to be ineligible or b) decline participation. The interviewer will also document the reason for ineligibility/refusal along with demographic information (gender, age, race, and ethnicity) to assess for selection bias.

ii. Scheduling process

[name], in collaboration with participating PAKSAB members and study staff determined the dates and times for the concept mapping sessions:

- a. 9/23 & 9/25
- b. 11/11 & 11/13
- c. 12/2 & 12/4

- Patients will be contacted by phone in a random order and will be recruited for participation in one of the three concept mapping groups using the IRB-approved phone scripts. Each group will have a mix of patients from the three care settings (acute, post-acute and primary care). The research team will schedule up to 30 patients per group for an end target of 16-20 total patient-participants in each group. Research team members will assign a study ID to each participant (Method is denoted with a “C”; Sessions are denoted by A, B, C; Participant setting numbers stay the same: 100’s, 200’s, 300’s (Examples: CA101, CB201, CC301)).

iii. Concept mapping process

The concept mapping process will consist of three steps that will take place over three sessions led by [name] and selected PAKSAB members. For each round of concept mapping, sessions 1 and 2 will take place at [name] on the 10th floor; session 3 will take place in the Department of Family & Community Medicine offices at [name]. Before each session, the research team should make the preparations described below.

Months Before

VOICe Study Procedures Manual V.6

- Contact the facilities manager to reserve training rooms in the computer lounge with enough computers for each participant
- Fill out a Project Activation Form (PAF) and email [name] to set up a new project with the CS Global Max annual license (as well as one test project, if a practice run is needed)
- If a new person will be responsible for the data analysis, designate them as the Project Administrator on the PAF and follow up to make sure they are set up with a log-on user name and password

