Our comparative analysis will start out with overall comparisons in which final thematic clusters from each of the three location-specific interview groups will be compared to the thematic clusters generated by the first CM group. This comparison will be a descriptive assessment of the presence/absence of each interview theme in the CM list. We will report proportions of the themes from each interview setting that were contained in the CM list as well as a detailed listing of each theme and in which lists it was present. Upon completion of this analysis, outputs from all three concept mapping groups will be aggregated and the same comparisons will be performed between the interview outcomes and the aggregated CM list.

We will then work with the RAC to study patterns in our data that emerge by setting, participant characteristics, mode of data collection, and any other categories as identified by the PAKSAB or RAC as potentially important. These analyses will be operationalized with the use of matrices and other data display techniques to study the potential contributions of these various characteristics to the outcomes identified within the proposed study. For example, a matrix of thematic clusters in columns and features of individuals (acute, post-acute, and primary care) in rows will allow us to explore consistencies and divergences in the data which are associated with these non-method based descriptors.

The efficiency of each method will be assessed by measuring overall resource utilization for conducting that method. We will determine the resource intensiveness for completion of a single concept mapping iteration through to completion, and for one set of interviews performed to saturation. The efficiency will be calculated based on the time required of research team and cost to conduct method.

We will also assess potential selection bias in who enrolled in interviews versus concept mapping using the data collected about who declines enrollment (gender, race, ethnicity, and age), and will assess on an on-going basis and at the end of the study how the enrolled patients compare to those who declined enrollment between the two groups. If we identify any systematic differences between the two groups, we will assess with our PAKSAB and our RAC how the difference(s) could have affected the thematic results obtained relative to the thematic results that we would have obtained.

E. Presentation and manuscript preparation

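### The one-group primary outcome uses the first concept mapping group only, so the plan does not show how much groups 2 and 3 each capture alone, although their theme sets will exist

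*Combined protocol and SAP*

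**What the plan says.** Section I.B lists as a primary outcome "Comprehensiveness of interviews as compared to one concept mapping group", and as a second primary outcome the same comparison against three groups.

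Section V.D carries out the first by checking which themes from "each of the three location-specific interview groups will be compared to the thematic clusters generated by the first CM group". The result is descriptive: for each interview setting, the proportion of its themes found in the CM list, plus "a detailed listing of each theme and in which lists it was present". For the second outcome, "outputs from all three concept mapping groups will be aggregated and the same comparisons will be performed" against the aggregated list.

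Section V.C processes each CM group separately, "thus generating three final sets of location-agnostic themes". On recruitment, section IV.ii says: "Patients will be contacted by phone in a random order and will be recruited for participation in one of the three concept mapping groups". It adds: "Each group will have a mix of patients from the three care settings". The target is 16-20 participants in every group.

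On timing, the milestone table in section I.C projects CM data collection (E4: "Conduct 3 sessions for each CM group (n=3CM groups, n= 60 participants") for completion by 12/31/2017. The start of the Aims 2 and 3 assessments (F1) is projected for 3/31/2018.

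**The concern.** The one-group proportion is the planned answer to a practical question: what share of the interview themes does one CM group recover? The project wants to inform best practice in study design, and section V.D costs efficiency for one CM iteration. A future user will therefore read the one-group figure as what a single group can be expected to deliver.

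One group shows what that group delivered. Two more groups will have been run under the same procedure, with their own theme sets, yet no sentence compares interviews with group 2 alone or group 3 alone, or reports a range across groups. What is at stake is how far the one-group figure can be generalised.

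**Working it through.** The documents give no expected proportion, theme count or capture rate for this comparison, so there is no planned figure to reproduce. Two checks were made on assumed inputs.

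**1. What the two planned figures determine.** For one interview setting, let g1, g2 and g3 be the proportions of its themes captured by each CM group, and u the proportion captured by the aggregate. A theme is taken to count in the aggregate if at least one group captured it (an assumption about how the lists are merged).

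- The gain u − g1 consists of themes that group 2 or group 3 captured and group 1 missed. A positive gain therefore shows that the groups differ in content.
- No group can exceed the aggregate, so g2 ≤ u and g3 ≤ u.
- Groups 2 and 3 must supply the gain between them, so g2 + g3 ≥ u − g1. Either one alone may be as low as 0 if the other supplies it all.
- Mean one-group capture therefore lies between [g1 + (u − g1)]/3 = u/3 and (g1 + 2u)/3.

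With assumed values g1 = 0.60 and u = 0.80:

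- g2 (or g3) lies between 0 and 0.80.
- The mean is at least 0.80/3 = 0.267.
- The mean is at most (0.60 + 1.60)/3 = 0.733.

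Enumerating all compatible cases with 10, 20 and 30 themes gave the same limits. These are logical bounds, not predictions. The upper side is capped and the lower side is left open. A zero gain would not settle the matter either: with g1 = u = 0.60, groups 2 and 3 could each lie anywhere from 0 to 0.60.

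**2. How large the spread might be.** K is the number of interview themes in a setting and p the mean chance that one CM group captures a theme. All inputs are assumed. With equal, independent capture, SD = √[p(1 − p)/K]. The expected best-to-worst gap among three groups is [Σ(1 − F³) − Σ(1 − F)³]/K, where F is the cumulative distribution of the number captured, summed over 0 to K − 1.

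| Assumption | K | p | SD of one group | Expected gap among three |
|---|---|---|---|---|
| Equal, independent | 10 | 0.80 | 0.126 | 0.208 |
| Equal, independent | 20 | 0.80 | 0.089 | 0.149 |
| Equal, independent | 30 | 0.90 | 0.055 | 0.091 |
| Equal, independent | 30 | 0.95 | 0.040 | 0.065 |
| Equal, independent | 30 | 0.98 | 0.026 | 0.038 |
| Unequal: 7 themes at 0.98, 3 at 0.38 | 10 | 0.80 | 0.092 | 0.149 |
| Unequal: 24 themes at 0.99, 6 at 0.54 | 30 | 0.90 | 0.044 | 0.073 |
| Group effect, within-group correlation 0.05 | 10 | 0.80 | 0.152 | 0.250 |
| Group effect, within-group correlation 0.05 | 30 | 0.90 | 0.086 | 0.138 |

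For the group effect, SD = √[p(1 − p)/K × (1 + 0.05(K − 1))]. For K = 10, p = 0.80 this is √(0.016 × 1.45) = 0.152.

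The gap runs from about 4 to 25 points across these rows, and the choice of p, K and correlation drives it. The table shows that the spread could be small or considerable; it does not estimate it.

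**The case against.** **The planned pair already carries information.** This stands. A reader might infer that the plan gives no indication at all of between-group variation. The documents do not support that: a rise from group 1 to the aggregate shows some difference, and the aggregate caps the other groups. The missing part is the share each other group captures alone, above all the low side.

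**Fixing the first group is a sound choice.** This also stands. It matches the one-group question and prevents choosing a favourable group later. Nothing suggests selective choice.

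**The groups are not randomised replicates.** Correct. Section IV.ii randomises the order of telephone contact; it does not state that patients are randomly allocated to groups. The groups run on different dates (starting 9/23, 11/11 and 12/2). A spread across them could include date, attendance or facilitation differences.

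**The plan leaves room for a per-group display.** In part. The theme listing could have a column for each CM group, but V.D does not say so, and the only CM lists it compares are the first group's and the aggregate. The matrices to be developed with the Research Advisory Council may use further categories, but CM group is not named. The third primary outcome, on comprehensiveness of concept mapping, has no separate analysis in V.D. None of these schedules the comparison, though no data are lost.

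**Three values estimate spread poorly.** True. Under a normal approximation, the 95% interval for an SD on 2 degrees of freedom runs from √(2/7.38) = 0.52 to √(2/0.0506) = 6.3 times the estimate. Three observed proportions are still more informative than one, but they should not be presented as a measure of reliability.

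**Conclusion.** The point holds as a cheap improvement to a descriptive analysis. V.D bases the one-group outcome on the first CM group and uses groups 2 and 3 only in the aggregate, and those two figures do not determine what either other group captures alone. That conclusion follows from the text and from the bounds above. It needs no assumption about capture rates, only that the aggregate is the union of the three lists.

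The size of the spread is unknown. A reader might take a gap of some 7 to 25 points from the rows with mean capture of 0.8 to 0.9. The documents do not support that or any other range: they give neither theme counts nor capture rates, and at 30 themes with capture of 0.98 the expected gap is 3.8 points. Nor do they support a claim that the first-group result is wrong or biased.

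**What to change.** In section V.D, keep the pre-specified first-group comparison as primary outcome 1 and the three-group aggregate as primary outcome 2. Add as a supplementary descriptive analysis:

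> The same comparison will be done separately for the second and third CM groups. For each interview setting, the three one-group proportions and their range will be reported beside the first-group result, and the theme listing will show presence in each CM group separately. The range will be described as observed variation only, because the groups ran on different dates and patients were not stated to be randomly allocated to them.

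The cost is 2 further CM lists × 3 interview theme lists = 6 presence/absence checks. The one-group proportions rise from 3 to 9, and the 3 aggregate proportions are unchanged. No new data are needed. On the projected milestone dates all CM data collection is complete before the Aims 2 and 3 work starts; if a later group is delayed, the first-group result can still be produced first.
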